5.2.3 Sample size and power estimates

Sample size and power calculations for this study are based upon the primary outcome of differences in weight gain between the two groups of infants. Using data from our recently completed analysis, in which infants 26 – 29 6/7 weeks gestation treated according to the algorithm were compared with historical controls, and based upon identifying a difference in weight Z-score of 0.25 at 36 weeks postmenstrual age, using a SD of 0.4 with an alpha = 0.05 and power of 0.8, we calculate we will need a total sample size of 82 patients (41 per group). With regards to the secondary outcome of EE, and based upon published data of EE estimated in preterm infants using the DLW method, a sample size of 41 patients per group will allow us to detect a 6% difference in EE, assuming an alpha = 0.05 and a power of 0.80. With regards to TBW, and based upon data from these same investigators who report a mean TBW of 80.8% body weight, with SD of 3.1%, this sample size will allow us to detect a difference in TBW of 2.0% between groups, assuming an alpha = 0.05 and a power of 0.80. To acknowledge for study drop out, we will plan to enroll up to 90 patients (plus 90 mothers for chart review).

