This algorithm was initiated as a standardized protocol to guide sodium supplementation at the University of Iowa Children's Hospital NICU in 2016 for infants 26 - 29 6/7 weeks gestation. The algorithm was applied to all infants excluding those with underlying renal abnormalities, or other conditions that may affect fluid and electrolyte balance. As expected, there was little relationship between serum and urine sodium concentrations at 2 weeks of postnatal age (Figure 2). Notable, a significant number of infants with

"normal" serum sodium concentrations had urine sodium concentrations that we interpreted as being consistent with sodium depletion, based on the algorithm.

To evaluate the impact of adapting the algorithm, data were compared for 50 infants, 26-29 6/7 weeks gestation cared for in the 2014-2015, prior to implementation of the algorithm and 40 infants cared for in 2016, after implementation of the algorithm. Results from this study have recently been published[44].

[figure not shown]

Figure 2. Serum sodium vs. urine sodium concentrations measured at 2 weeks postnatal

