Twenty-three (58%) of infants had initial (2-week measurement) urine Na concentration warranting supplementation; while another 7 of infants had low urine sodium concentration] at 4 wk, warranting supplementation. Thus, 75% of infants cared for using this algorithm received sodium supplementation above that in their normal diet. Daily Na intake was similar at 2 wk in both cohorts, but significantly greater (p <0.05) at 4, 6 and 8 wk in the 2016 vs. 2014–2015 cohort (Table). Weight gain, determined as change in weight Z-score between 2 and 8 wk of age, was significantly greater in 2016 vs. 2014–2015 cohort (0.32 ± 0.06 vs. -0.01 ± 0.08, p<0.01). Caloric, protein and total fluid intakes as well as daily urine output were similar between cohorts at the measured time points of 2, 4, 6 and 8 weeks of age (Table). Use of the algorithm did not negatively impact respiratory morbidity at either 28 days of postnatal age (or at 36 weeks postmenstrual age (2014-2015 cohort: 60% receiving supplemental oxygen; 2016 cohort: 48% receiving supplemental oxygen). Since initiating use of this algorithm, no infant has required sodium supplementation to be discontinued due to hypernatremia (serum [Na] >144 mEq/L). These data suggest the physiologically based algorithm to individualize identification of need for sodium supplementation in the preterm infant resulted in increased sodium intake and growth in this population. Given the potential benefits of this approach on growth and ultimately neurodevelopmental outcome, a randomized controlled

Table. Sodium, caloric and protein intakes at increasing postmenstrual ages

trial to evaluate the efficacy of this approach is needed.

Postmenstrual Age							
2 wk	4 wk	6 wk	8 wk				
3.5 ± 0.2	3.8 ± 0.2	3.8 ± 0.2	3.2 ± 0.1				
3.7 ± 0.3	5.3 ± 0.2*	5.7 ± 0.3*	4.4 ±0.2*				
112 ± 3	119 ± 3	119 ± 3	125 ± 4				
115 ± 3	116 ± 2	121 ± 2	120 ± 2				
4.1 ± 0.1	3.9 ± 0.1	4.2 ± 0.1	4.0 ± 0.1				
4.2 ± 0.1	4.0 ± 0.1	4.0 ± 0.1	3.9 ± 0.1				
140 ± 2	147 ± 1	146 ± 1	148 ± 3				
139 ± 2	146 ± 2	147 ± 1	149 ± 2				
73 ± 3	83 ± 2	86 ± 3	93 ± 2				
75 ± 2	85 ± 2	85 ± 3	95 ± 3				

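### The SD of 0.4 behind the stated 80% power has no documented source, and the only pilot weight Z-score spread shown points to about 0.48–0.49 across both cohorts

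*Combined protocol and SAP*

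**What the plan says.** Section 5.2.3 opens its calculation with "Using data from our recently completed analysis", meaning the comparison of algorithm-treated infants with historical controls. It targets a weight Z-score difference of 0.25 at 36 weeks, "using a SD of 0.4 with an alpha = 0.05 and power of 0.8", and arrives at 82 patients, 41 per group. It then adds: "To acknowledge for study drop out, we will plan to enroll up to 90 patients". No derivation of 0.4 and no sensitivity to it are given.

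The pilot is described in Section 2.2 under the preliminary data: "data were compared for 50 infants, 26-29 6/7 weeks gestation" before the algorithm, against 40 infants treated with it in 2016. Weight gain, "determined as change in weight Z-score between 2 and 8 wk of age", is reported as "0.32 ± 0.06 vs. -0.01 ± 0.08, p<0.01", algorithm cohort first. The ± values carry no label. This is the only spread for a weight Z-score anywhere in the document.

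Section 3.2.3 allocates infants 1:1. Section 3.2.8 defines the primary outcome as change from 2 weeks of age to 36 weeks or transfer. Section 5.2.2 adjusts for gestational age and names no other covariate.

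**The concern.** The required sample size rises with the square of the SD, so 0.4 is the input on which the stated power mainly depends. It is presented in a sentence that rests on the pilot, yet it resembles the algorithm cohort alone (about 0.38). Half of this trial receives usual care, which was the more variable pilot cohort. If the spread across both arms is nearer 0.48–0.49, a true difference of 0.25 would be missed about 36–38% of the time at 41 per group instead of 20%. A null result could then be taken as stronger evidence against the planned effect than it is.

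**Working it through.** **Reproducing the plan's figure.** n per arm = 2 × (1.960 + 0.842)² × 0.4² / 0.25² = 40.2, rounded up to 41, or 82 in total. The two-sided formula is needed; a one-sided test would give 32 per arm. Two-sample t power at 41 per arm and SD 0.40 is 79.8%. There is no arithmetic error.

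**What the ± values are.**
- As standard errors: t = 0.33 / √(0.06² + 0.08²) = 3.3, p = 0.0014 on 88 df, which fits the printed p<0.01.
- As SDs: t = 0.33 / √(0.06²/40 + 0.08²/50) = 22.4, which is not credible beside p<0.01.

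The intake table in the same section agrees. Its row labels are lost in the text available, so the rows are identified from the table title and the values.
- The text says "Daily Na intake was similar at 2 wk in both cohorts". For 3.5 ± 0.2 vs 3.7 ± 0.3, p = 0.58 as standard errors but 0.0005 as SDs.
- It also says "Caloric, protein and total fluid intakes as well as daily urine output were similar between cohorts". For 8-week calories, 125 ± 4 vs 120 ± 2, p = 0.27 as standard errors but below 0.0001 as SDs.

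**Implied SDs, assuming all 40 and 50 infants had both weights.**
- Algorithm: 0.06 × √40 = 0.379 (0.35–0.41 with rounding of the standard error).
- Usual care: 0.08 × √50 = 0.566 (0.53–0.60).
- Combined: √[(0.379² + 0.566²)/2] = 0.482 with equal weights; √[(39 × 0.379² + 49 × 0.566²)/88] = 0.492 weighted by degrees of freedom.
- With the algorithm arm at 0.379, an equal-weight combined SD of 0.40 would need a usual-care SD of √(2 × 0.16 − 0.379²) = 0.42.

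**Power for 0.25** (two-sample t, two-sided 0.05, noncentrality 0.25 / [SD × √(2/n)]):

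| SD | 41 per arm | 45 per arm |
|---|---|---|
| 0.40 | 80% | 84% |
| 0.482 | 64% | 68% |
| 0.492 | 62% | 66% |
| 0.55 | 53% | 57% |

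- Rounding of both standard errors puts the combined SD at 0.448–0.525 and power at 57–70% (41 per arm) or 61–74% (45 per arm).
- Sampling error: an approximate 95% interval for the equal-weight SD at the printed values (chi-square, Satterthwaite df about 82) is 0.42–0.57, or power of about 50–76% at 41 per arm.
- The difference detectable with 80% power is 0.30–0.31 at 41 per arm and 0.29 at 45.
- For the pilot's own difference, 0.32 − (−0.01) = 0.33, power at 41 per arm is 85–87%.

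**What would bring the SD back to 0.40.**
- Missing weights: if the same share of each cohort was measured (an assumption), the share must be (0.40/0.482)² = 69% or (0.40/0.492)² = 66%, or lower. At the lower rounding limit it is 76–80%. With 90%, 80% and 70% measured, power at the printed values is 67–69%, 72–74% and 77–79%.
- Covariate adjustment: the covariates must explain 1 − 0.69 = 31% to 1 − 0.66 = 34% of the variance (20–42% with rounding).

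**The case against.** The strongest reply is that the two spreads describe different quantities. The pilot figure is change over 6 weeks, from 2 to 8 weeks of age, in infants born at 26 to 29 6/7 weeks. The trial's window runs to 36 weeks: 36 − 27 = 9 weeks for birth at 25 0/7, but only 6 to 4.1 weeks for births at 28 0/7 to 29 6/7. The trial also adds 25-week infants, and the spread in historical controls may not carry over to concurrent ones. The 36-week SD could be larger or smaller, and the pilot dataset may contain a 36-week SD of 0.4 that Section 2.2 does not print. All of this stands. A reader might infer that Sections 2.2 and 5.2.3 contradict each other; they do not, because both SDs can be true.

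The implied SD is also imprecise. It comes from 40 and 50 infants, and some 8-week weights may be missing, since 8 weeks of age is already 36 weeks or later for births at 28 weeks and above. At the printed values with everyone measured, 0.40 lies just outside the sampling interval. If 90% of each cohort was measured, the interval is about 0.39–0.55 and power about 54–81%. So 62–64% should not be treated as a firm figure.

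Two further points have weight. Planning on 0.25 is more cautious than the pilot's 0.33, for which power would be adequate on either SD. And the final estimate will carry its own precision from the observed residual SD, which limits how far a null result could mislead.

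None of this supplies a source for 0.4. A different window is a reason to show the matching SD, and the plan does not do so.

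**Conclusion.** The stated 80% power for 0.25 is not supported by the pilot data shown. Those data give a combined SD of about 0.48–0.49, against the 0.4 entered. If that spread applied to the 36-week change, power would be about 62–64% at 41 per arm and 66–68% at 45, with the wider ranges given above. This rests on four assumptions: the ± values are standard errors, which the printed p-value and the similarity statements support; all 40 and 50 infants were measured; the 2–8 week spread carries over to the 36-week outcome; and covariates remove little variance.

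A reader might go on to infer that the trial's true power is 62–64%, or that it must enrol the 59–61 per arm that would restore 80% at that SD. The documents do not support either, because the second and third assumptions cannot be checked from them. The point should be fixed, with medium confidence in the size of the shortfall.

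**What to change.** In Section 5.2.3, recompute the SD from the unrounded data of both pilot cohorts for the change from 2 weeks of age to 36 weeks, using the infants actually measured. State its source, the number of infants, and whether it is raw or covariate-adjusted (if adjusted, with the covariates and R²). From that SD, restate the power for 0.25 and the difference detectable with 80% power, at 41 and 45 per arm. If the documented SD is 0.4, the present statement can stay.

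If no 36-week SD can be documented, replace the single 80% figure with power over SDs of 0.40 to 0.55. At 41 per arm this is about 80% at 0.40, 62–64% at 0.48–0.49 and 53% at 0.55. Note beside it that the 2–8 week spread of both pilot cohorts falls near 0.48–0.49, assuming complete measurement.

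In Section 2.2, label the ± values and give the number of infants in each cohort with both a 2-week and an 8-week weight.

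The cost is one paragraph in 5.2.3 and a label and counts in 2.2. The stated power may become less favourable. The sample size need not change.

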5.3 DATA SAFETY AND MONITORING PLAN

A Data Safety and Monitoring Committee (DSMC), headed by [name], Professor of Pediatrics, University of Iowa Carver College of Medicine will monitor the progress of the study when 25%, 50% and 75% of the trial subjects have reached hospital discharge. [name], who has extensive experience with DSMCs, will be responsible for recruiting the necessary individuals with expertise in neonatology, biostatistics, bioethics and clinical trials to establish the DSMC. The DSMC will review accumulated blinded study data to ensure that the intervention is not leading to harm. If there is a significant imbalance of secondary outcome rates between the study arms, the proper course of action will be discussed by the study PIs and the DSMC. The DSMC will not be charged with assessing efficacy before conclusion of the trial; therefore, no loss of alpha will result from the planned interim safety analyses.

Safety outcomes include incidence of mortality up through 36 weeks PMA, BPD, and ROP. The DSMC may request other outcomes at their prerogative. The DSMC will examine other safety outcomes, including all reported deaths and serious adverse events by treatment group in considering a recommendation to suspend the trial for safety reasons.

SECTION 5. REFERENCES

- 1. Fenton, T.R. and J.H. Kim, A systematic review and meta-analysis to revise the Fenton growth chart for preterm infants. BMC Pediatr, 2013. **13**: p. 59.
- 2. Griffin, I.J., et al., *Postnatal growth failure in very low birthweight infants born between 2005 and 2012.* Arch Dis Child Fetal Neonatal Ed, 2016. **101**(1): p. F50-5.
- 3. Horbar, J.D., et al., Weight Growth Velocity and Postnatal Growth Failure in Infants 501 to 1500 Grams: 2000-2013. Pediatrics, 2015. **136**(1): p. e84-92.
- 4. Ehrenkranz, R.A., et al., *Growth in the neonatal intensive care unit influences neurodevelopmental and growth outcomes of extremely low birth weight infants.* Pediatrics, 2006. **117**(4): p. 1253-61.
- 5. Ehrenkranz, R.A., et al., Longitudinal growth of hospitalized very low birth weight infants. Pediatrics, 1999. **104**(2 Pt 1): p. 280-9.
- 6. Franz, A.R., et al., *Intrauterine, early neonatal, and postdischarge growth and neurodevelopmental outcome at 5.4 years in extremely preterm infants after intensive neonatal nutritional support.* Pediatrics, 2009. **123**(1): p. e101-9.
